13.5 DATA MONITORING COMMITTEE (DMC)

A DMC will provide ongoing independent review of the data, further ensuring the continued safety of subjects, ongoing adjudication of study endpoint events, as well

as the validity and scientific merit of the trials. The DMC consists of up to three voting members, with relevant expertise. The DMC members are not directly related to the study.

14 DEVICE ACCOUNTABILITY

The investigator shall maintain adequate records of the receipt and disposition of all devices per local institutional procedure and regulations.

15 PROTECTION OF HUMAN SUBJECTS

15.1 STATEMENT OF COMPLIANCE

This study will be conducted in compliance with the current ICH E6 GCP, the ethical principles of the Declaration of Helsinki, current FDA GCP guidelines, and any additional national or IRB/IEC or CA-required procedures, whichever represents the greater protection for the individual.

15.2 INFORMED CONSENT

This study will be conducted in compliance with current ICH E6 GCP pertaining to informed consent, the current CFR (Title 21, Parts 50). To participate in the study, the subject must sign and date the ICF after having been informed about the nature and purpose of the study, participation and termination conditions, risks, and benefits, before initiation of any study-related procedures. A copy of the signed ICF must be provided to the subject. If applicable, the ICF will be provided in certified translation for non-English-speaking subjects. Signed ICFs must remain in the subjects' study files and be available for verification by the Sponsor or Sponsor representative at any time.

16 STATISTICAL CONSIDERATIONS

16.1 GENERAL ANALYSIS PRINCIPLES

All primary endpoint analyses will be conducted under the principle of "Intention-To-Treat" (ITT), where each subject randomized to a treatment group who has met all inclusion/exclusion criteria and had a mapping and/or ablation catheter inserted shall be considered part of the ITT group. As a secondary exploratory analysis, a "Per Protocol" (PP) analysis may be performed with a subgroup of the ITT group who have no major protocol deviations reported.

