8 SELECTION, DISCONTINUATION, AND WITHDRAWAL OF SUBJECTS

8.1 SELECTION CRITERIA

The criteria listed below shall be used to determine if a participant is eligible for entry into the study. A subject must meet ALL of the study inclusion criteria and NONE of the study exclusion criteria in order to be considered eligible for participation.

A. *Inclusion Criteria*

Subjects are required to meet the following inclusion criteria:

1. Male or female 18 – 80 years of age.
2. Experiencing at least two (2) documented episodes of persistent atrial fibrillation (including long standing persistent) during the 3 months preceding study entry with clinical indication for AF ablation per guidelines. At least one episode should be documented by rhythm strip or ECG. Persistent AF is defined as continuous AF that is sustained beyond seven days (long standing persistent is >12 months). Episodes of AF in which a decision is made to electrically or pharmacologically cardiovert the patient after ≥48 hours of AF, but prior to 7 days, should also be classified as persistent AF episodes.
3. Refractory, contraindicated, or intolerant to Class I or III anti-arrhythmic medications. Drug doses must be therapeutic and stable.
4. Novel Oral Anticoagulant (e.g. dabigatran, rivaroxaban, apixaban), Warfarin (therapeutic INR ≥ 2.0 for at least three weeks prior to randomization), or other similar standard-of-care oral anticoagulant therapy is required (aspirin is not considered similar) for those subjects who meet two or more of the following criteria:
 - a. Age 65 years or older
 - b. Diabetes
 - c. Coronary artery disease (CAD)
 - d. Congestive heart failure
 - e. Hypertension with systolic >165 mm Hg
5. Willingness and able to remain on anti-coagulation therapy for a minimum of 3 months post procedure for all subjects and at least 12 months post procedure if the patient is on anti-coagulation pre-procedure or has CHADS2 score ≥ 2.
6. Left atrial diameter < 6.0 cm via transthoracic echo; or <6.5 cm via CT or MRI up to 3 months pre-procedure with documented image of largest dimension, or intraprocedural ICE or atrial angiogram if CT/MRI not available.
7. Sustained AF (>5 min uninterrupted) during the electrophysiology procedure. If the subject is not experiencing spontaneous, sustained AF, it may be induced by burst pacing (typically from the coronary sinus) with or without isoproterenol infusion in conventional clinical fashion.

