8. Women without childbearing potential, (surgically sterile or have been without a period for 12 months), or women of childbearing potential who are not pregnant per a serum HCG laboratory test.
9. Willingness, ability and commitment to participate in baseline and follow-up evaluations without participation in another clinical trial which may confound the results of this study, unless approved by the Sponsor.
10. Signed patient informed consent form.

B. *Exclusion Criteria*

Subjects must NOT meet any of the following exclusion criteria:

1. Presence of structural heart disease of clinical significance including:
 - a. Coronary artery disease with either:
 - i. Coronary artery bypass surgery (CABG) within the last 180 days (six months), or
 - ii. Stable/unstable angina or ongoing myocardial ischemia.
 - b. Congenital heart disease where either the underlying abnormality or its correction prohibits or increases the risk of ablation.
2. NYHA Class IV.
3. Ejection fraction < 35% (within previous 3 months).
4. Previous AF ablation.
5. History of myocardial infarction (MI) within the past three months.
6. Any concomitant arrhythmia or therapy that could interfere with the interpretation of the results from this study.
7. ASD closure device, LAA closure device, prosthetic mitral or tricuspid valve, and permanent pacemakers or defibrillator leads.
8. Untreatable allergy to contrast media.
9. Severe electrolyte abnormalities at time of the ablation procedure or atrial fibrillation secondary to electrolyte imbalance, thyroid disease, or reversible non-cardiac cause.
10. Atrial fibrillation from a reversible cause (e.g., surgery, hyperthyroidism, pericarditis).
11. Contraindication to Heparin and Warfarin/other novel oral anticoagulants (e.g. dabigatran, rivaroxaban, apixaban).
12. History of pulmonary embolus within one year of enrollment.
13. Acute pulmonary edema.
14. Atrial clot/thrombus on imaging such as on a trans-esophageal echocardiogram (TEE) performed within 72 hours of the procedure if deemed appropriate by investigator.
15. History of a cerebrovascular disease (including stroke or TIA).

16. Any anticipation of cardiac transplantation or other cardiac surgery within the next 12 months.
17. History of documented thromboembolic event within the past one year that affects the ability to perform the procedure.
18. Diagnosed atrial myxoma.

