8.3 MOMENT OF ENROLLMENT

The subject will be considered "enrolled" in the study after the subject has met all inclusion and exclusion criteria, has signed the study informed consent form, and has completed the baseline assessments.

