8.4 RANDOMIZATION AND SUBJECT IDENTIFICATION

Randomization will occur if the subject is deemed eligible following screening assessments and has signed the informed consent form. Subject identification number will be assigned at the time of randomization and the identification number will be retained throughout the study. No personal identifying information will be included on the case report forms.

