10.2 STUDY PROCEDURE

The subject will be scheduled to undergo study treatment after the subject has met all inclusion and exclusion criteria, has signed the study informed consent form, and has completed the baseline assessments. Once enrolled in the study, the subject will be randomized to undergo either conventional AF treatment with ablation, or FIRM-guided procedure followed by conventional AF ablation.

A. *Pre-procedure Preparation*

Just prior to and/or during the procedure, a glycoprotein IIb/IIIa inhibitor or other platelet inhibitor may be administered if it is standard practice. The insertion of the FIRMap catheter or performing transseptal puncture, whichever comes first, will be followed immediately by an IV heparin bolus, followed by repeated heparin administration, adjusted as necessary to achieve and maintain an ACT above 300 seconds.

B. *Intra-procedure Guidelines*

During the procedure, the following actions should be taken and appropriate data collected. Table 6.

Table 6 – Intra-Procedure Guidelines

Parameter	Description
Vascular access	Under sterile technique, the right and/or left femoral veins may be cannulated via Seldinger, or percutaneous approach. Other vascular access also may be obtained based upon physician judgment.
Reference catheter placement	Reference catheters (including 64-pole FIRMap catheter(s)) may be inserted and placed within the heart to record signals as clinically required at the discretion of the physician.
Access to left atrium	Access to the left atrium should be according to the institution's standard practice.
Anticoagulation	Upon insertion of 64-pole FIRMap catheter or transseptal puncture (whichever comes first), an IV heparin bolus should be administered, followed by repeated heparin administration, adjusted as necessary to achieve and maintain an ACT above 300 sec.
Catheter placement	Catheters may be inserted and used according to the institution's standard practice.
Source arrhythmia diagnosis	After obtaining at least 1 minute of continuous electrograms from the 64-pole FIRMap catheter either simultaneously or sequentially in the right and left atria, these electrogram data will be transferred to the Topera RhythmView® system. This will then produce FIRMap displays which will be interpreted by the operator to determine which locations have focal or rotor rhythms that could be sources of the AF.

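### The set called ITT is a modified ITT set, and the protocol does not settle whether randomisation comes before the one criterion that can be judged only during the procedure

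*Protocol*

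**What the plan says.** Protocol section 16.1 applies the intention-to-treat label to every primary endpoint analysis and defines the set as "each subject randomized to a treatment group who has met all inclusion/exclusion criteria and had a mapping and/or ablation catheter inserted". The per-protocol (PP) set is optional and exploratory. It is the part of this ITT set with no major deviation. Section 13.4 counts a departure from the entry criteria as a major deviation. Section 16.2 C uses the same ITT set as the denominator for acute safety.

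On the order of events:

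- Section 8.1, inclusion 7, requires "Sustained AF (>5 min uninterrupted) during the electrophysiology procedure". Table 6 in section 10.2 says that a patient in whom AF cannot be sustained is ineligible and goes on to conventional ablation.
- Section 8.1, inclusion 6, allows left atrial size to be documented by imaging during the procedure as an alternative.
- Section 8.3 regards a subject as enrolled "after the subject has met all inclusion and exclusion criteria, has signed the study informed consent form, and has completed the baseline assessments".
- Section 8.4 states: "Randomization will occur if the subject is deemed eligible following screening assessments and has signed the informed consent form".
- Section 10.2 states "The subject will be scheduled to undergo study treatment after the subject has met all inclusion and exclusion criteria", and then "Once enrolled in the study, the subject will be randomized to undergo either conventional AF treatment with ablation".

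**The concern.** An ITT analysis compares the groups as randomised. The set in section 16.1 adds two conditions that can be applied after allocation: the subject proved eligible, and a catheter was inserted. A reader of the results would take the primary comparison for ITT when it is not.

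The eligibility condition matters most for inclusion 7, because the judgement is made in the lab. If allocation has already happened, the operator who decides whether AF can be sustained may know the arm, and that decision determines whether the subject counts in the primary effectiveness and safety comparisons. The protocol's statements on when randomisation happens do not show whether this can occur.

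**Working it through.** **1. The analysis sets.** Section 16.1 ITT = randomised, and all criteria met, and catheter inserted. Section 16.1 PP = ITT minus major deviations. Section 13.4: entry-criterion deviations are major. For a subject whom the site entered wrongly, the eligibility part of the PP filter has therefore already been applied inside ITT. Since PP is a subset of ITT, neither set contains all randomised subjects.

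**2. The time of randomisation.** Inclusion 7 is known only during the procedure.

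- Section 10.2 schedules the procedure after all criteria are met. This cannot hold literally for inclusion 7.
- Sections 8.3 and 10.2 together give: all criteria met, then enrolled, then randomised. Taken literally, randomisation falls inside the procedure.
- Section 8.4 gives: screening assessments and consent, then randomised. Taken literally, randomisation falls before the procedure.

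No passage names a clock time. The conflict appears once inclusion 7 is counted among all criteria. Figure 1 is not shown and may mark the point.

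**3. The two branches.** If randomisation follows confirmation of sustained AF, inclusion 7 removes no randomised subject. The label and the other exclusions remain. If randomisation precedes it, non-sustainers are removed after allocation.

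**4. Size under the second branch (illustration only).** From the documents: up to 350 subjects at 1:1, so 350/2 = 175 per arm, and a two-sided alternative. Assumed, because alpha is redacted and no rates are given: alpha 0.05; no true effect; 50% success in sustainers; a share q = 2% to 20% not sustainable; success in these higher by a = 10 to 30 points; k = share of non-sustainers kept in an arm.

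- Arm mean = [(1−q)·0.50 + q·k·(0.50+a)] / [(1−q) + q·k]
- Arm size = 175·[(1−q) + q·k]
- Type I error = P(|Z + bias/SE| > 1.96), unpooled SE

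Example with q = 0.10, a = 0.20, one arm k = 0 and the other k = 0.5. The first arm has mean 0.500 and n = 157.5. The second has (0.450 + 0.035)/0.95 = 0.5105 and n = 166.25. The bias is 1.05 points, the SE is 0.0556, the ratio is 0.19 and the type I error is 5.4%.

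Over the whole range:

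- Equal exclusion in both arms: bias 0, type I error 5.0%.
- One arm excludes all, the other half: 0.1 to 3.3 points, 5.0% to 8.9%.
- One arm excludes all, the other none (extreme bound): 0.2 to 6.0 points, 5.0% to 18.6%.

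**5. Safety under the second branch.** Assume equal exclusion and an SAE rate s of 2% to 8% in both arms. Subjects leaving: 175q = 3.5 to 35 per arm. Events leaving: 175·q·s = 0.07 to 2.8 per arm. The expected difference does not change. The 95% interval widens by 1/√(1−q) = 1.01 to 1.12. At s = 5%, the half-width 1.96·√(2·0.05·0.95/175) = 4.57 points becomes 4.61 to 5.11. At the extreme bound, with SAE rates in non-sustainers half or double, the bias is q·s/2 to q·s = 0.02 to 1.6 points.

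**The case against.** The strongest reply is that sections 8.3 and 10.2 with Table 6 can be read so that a non-sustainer is never enrolled and hence never randomised. That reading is possible, and under it the selection problem from inclusion 7 disappears. It does not repair the scheduling sentence in section 10.2 or the looser wording of section 8.4, and the eligibility and catheter clauses stay in section 16.1.

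A second reply is that Table 6 applies one rule to both arms. This also stands: with equal exclusion the illustrated bias is zero.

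Some stronger readings are tempting but not supported:

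- That PP removes all eligibility failures, so ITT and PP coincide. Section 13.4 defines a deviation as conduct not according to protocol, and a non-sustainer handled as Table 6 directs may not be one. PP also removes other major deviations, such as consent and randomisation errors.
- That several criteria are judged only at the procedure. Only inclusion 7 is. Inclusion 6 merely may be. Exclusion 9 ("Severe electrolyte abnormalities at time of the ablation procedure") does not say that the abnormality is detected only then, and the TEE of exclusion 14 is a baseline item.
- That the INR period fixes the time. It runs "for at least three weeks prior to randomization" in section 8.1 and up to the procedure in section 10.1, and these agree if both fall on one day.
- That SAEs of excluded subjects go unreported. Sections 11, 11.2 and 13.5 still provide for recording and review. Only the randomised comparison is affected.

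**Conclusion.** Two things follow from the text alone. The set used for all primary effectiveness and safety analyses is a modified ITT set under the name ITT, with no analysis of all randomised subjects named. And sections 8.3, 8.4 and 10.2 cannot all be followed for inclusion 7, so they must be reconciled.

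The rest is conditional. Only if randomisation precedes induction does inclusion 7 remove subjects after allocation, and only exclusion that differs by arm and is related to outcome biases the comparison, in either direction. A reader might infer that the primary result is biased or that the type I error reaches 18.6%. The documents do not support this: that figure needs one arm to ignore a rule that binds both, at the top of the assumed ranges. At 10% non-sustainers with success 20 points higher, excluding all in one arm and half in the other gives 1.1 points and 5.4%. The true size is unknown. The point should be fixed because the rule allows avoidable selection and the repair is cheap.

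**What to change.** 1. State one randomisation point consistently in sections 8.3, 8.4, 10.2 and Table 6, preferably after the criteria judged at the procedure are confirmed. Report SAEs of subjects who are then not randomised descriptively. The small cost is web randomisation in the lab with the FIRM equipment ready before allocation.
2. Delete both the eligibility and the catheter clauses from the ITT definition, so that primary effectiveness covers all randomised subjects as assigned. Run primary safety on all randomised subjects with any catheter inserted, regardless of eligibility. Keep the present section 16.1 set as a sensitivity analysis named modified ITT, and do not rely on the optional PP set for non-sustainers. Because section 10.3 counts follow-up from the procedure day, a time origin and outcome rule are needed for randomised subjects who never start a procedure (section 8.5 allows withdrawal before treatment).
3. Report by arm and reason every randomised subject left out of any analysis.

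If randomisation stays before the procedure, the downside is dilution, since Table 6 sends non-sustainers to conventional ablation in either arm. Assume 65% v 50% success in sustainers, 70% in non-sustainers, 175 per arm and two-sided 0.05. Kept: rates (1−q)·0.65 + q·0.70 v (1−q)·0.50 + q·0.70 with n = 175. Excluded: 0.65 v 0.50 with n = 175(1−q). Power, kept v excluded, is about 80% v 81% at q = 2%, 78% v 80% at 5%, 74% v 78% at 10% and 64% v 73% at 20%. With randomisation after confirmation and 175 sustainers per arm it is about 82%, another reason to prefer that order. Apart from this, the cost is mainly wording.

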Total RF ablation time	
Total RF ablation time as measured by total time of ablation lesion applications, from first ablation lesion to end of last lesion, will be documented. These values will be noted in both the FIRM-guided and conventional ablation groups. If ablation for AT/atrial flutter is pursued, this ablation time will be documented separately

Total procedure time	
Total procedure time defined as: time from insertion of first sheaths for vascular access to removal of sheaths.

Medication administration	
Cardiac medications administered during the procedure including drug name, dosage, and indication and will be recorded.

Devices and equipment	
Devices and equipment used during the procedure including access devices, diagnostic and ablation catheters, and mapping equipment type will be recorded.

D. Post-procedure & Discharge Requirements

The measurements and evaluations that will occur at post-procedure are provided below.

- Post-ablation and following recovery from anesthesia, subjects will be monitored until stable.
- Once the sheaths have been removed and hemostasis has been achieved, heparin or LMWH will be restarted along with oral anticoagulation (warfarin or novel oral anticoagulants (e.g. dabigatran, rivaroxaban, apixaban)).

The platelet inhibitor (if administered during the procedure) and heparin or LMWH will be continued until the INR exceeds 2.0 (in the case of warfarin use for longer term oral anticoagulation).

Oral anti-coagulation will continue for at least three months after the procedure. Subjects who were on oral anticoagulation pre-procedure will be maintained on anticoagulation for the duration of the study.

Note: Oral Glycoprotein IIb/IIIa Inhibitors use is discouraged during the follow-up period.

- Post-procedure drug therapy will include re-initiation and/or continuation of any pre-procedure cardiac medications including all anti-arrhythmic drugs used for the treatment of atrial flutter or other arrhythmias/cardiac diseases. Supplemental anti-arrhythmic medications will be administered under the direction of the investigator and documented in the appropriate section(s) of the case report forms.

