11.3 ANTICIPATED ADVERSE EVENTS

Table 9 – Anticipated Adverse Events

Description	Description
Discomfort due to insertion/removal of vascular sheaths beyond what is normally observed	Ventricular arrhythmia requiring defibrillation
Hemorrhage and/or hematoma at sheath insertion requiring evacuation or transfusion	Cardiac tamponade due to perforation
Extremity weakness, swelling, and/or pain	
Discomfort and/or damage to the skin, muscles, or nerves due to remaining in a supine position for an extended period of time.	Nerve injury (diaphragmatic paralysis, pyloric spasm, gastric hypomotility)
Complete AV block	Air embolism
Nausea /vomiting	Allergic reaction
Headache different from baseline	Endocarditis
Hypertension >180 mm Hg systolic (repeated measures)	Esophageal-atria fistula
Hypotension <80 mm Hg systolic (repeated measures)	Hemothorax
Brief “black out” periods	Pericarditis
Shortness of breath/Dyspnea	Pseudo aneurysm
Feeling of chest pain, skipped beats, and/or rapid heart rate different from baseline	Pulmonary vein stenosis
Damage to skin from prolonged exposure to x-rays	Radiation injury
New arrhythmias (not previously documented)	Renal failure from IV contrast

Arterial injury requiring intervention	Respiratory failure
Thromboembolism	Stroke/TIA
Local/systemic infection	Valvular damage
Pneumothorax	Pleural effusion
AV fistula	Pulmonary edema
Thrombophlebitis	Anemia requiring transfusion
Pulmonary embolism	Vasovagal reaction
Myocardial infarction	New pericardial effusion >1 cm
Discomfort and/or damage to the skin, muscles, or nerves due to percutaneous access in excess of usual	Death (must be reported within the regulation of serious adverse events)
Left heart access via trans-septal puncture has known potential adverse events of: cardiac perforation, cardiac tamponade, and embolic events*.	

* Literature reviews have demonstrated that the risk of such events are <1%. Mullins, Charles E. "Trans-septal left heart catheterization: Experience with a new technique in 520 pediatric and adult subjects." *Pediatric Cardiology*, v. 4, pgs. 239-246 (1983).

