This endpoint will be evaluated using a Chi-Square test of independence, the proportions assumed to be binomial for each group.

C. Acute Safety (Primary safety endpoint)

The acute safety success of either treatment arm is defined as freedom from serious adverse events related to the procedure within ten (10) days of the index procedure. The proportion of successes in each arm will be calculated as follows:

$$\frac{n}{N}$$

Where:

n = the total count of subjects presenting freedom from serious adverse events related to the procedure within ten (10) days of the index procedure.

N = the total count of subjects in that arm in the ITT group

The statistical hypothesis for this endpoint is operationalized as follows:

$H_0: p_E = p_C$

$H_A: p_E \neq p_C$

Where:

p_E = the proportion of "successes" in the FIRM arm

p_C = the proportion of "successes" in the conventional ablation control arm

This endpoint will be evaluated using a Chi-Square test of independence, the proportions assumed to be binomial for each group.

D. Long-Term Safety (Primary safety endpoint)

Long-term safety is defined as freedom from procedure-related serious adverse events (SAEs) (including those related to repeat procedures) within one year of the initial procedure.

The statistical hypothesis for this endpoint is operationalized as follows:

$H_0: p_E = p_C$

$H_A: p_E \neq p_C$

$\alpha =$

Where:

p_E = the proportion of subjects free from serious adverse events related to the procedure (including from any repeat procedures required) within one year of the index procedure in the FIRM arm

p_C = the proportion of subjects free from serious adverse events related to the procedure (including from any repeat procedures required) within one year of the index procedure in the conventional ablation control arm

The proportion of events in each treatment arm shall be evaluated relative to their respective primary endpoint using both Chi-Square (Binomial, 1df) and by Kaplan-Meier survival estimation. Each evaluation will include 95% confidence intervals.

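### Both primary safety endpoints leave out a procedure-related SAE that ends the case before a mapping or ablation catheter is inserted

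*Protocol*

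**What the plan says.** Section 16.1 names its set intention-to-treat and applies it to all primary endpoint analyses. Membership has three conditions: the subject was randomised, met all inclusion and exclusion criteria, and "had a mapping and/or ablation catheter inserted shall be considered part of the ITT group".

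The safety endpoints are primary (Table 1 in section 7.1; 16.2 C and D). For acute safety the denominator is explicit: "N = the total count of subjects in that arm in the ITT group". For long-term safety 16.2 D gives no other denominator, so the general rule of 16.1 governs. The protocol defines no separate safety population.

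On timing, section 8.4 states: "Randomization will occur if the subject is deemed eligible following screening assessments and has signed the informed consent form". Table 7 in section 10.2 defines total procedure time as "time from insertion of first sheaths for vascular access to removal of sheaths". On the hazards of the early steps, section 11.1 classes a catheter-site haematoma or AV fistula that needs transfusion or surgical repair as serious. Table 9 in section 11.3 adds: "Left heart access via trans-septal puncture has known potential adverse events of: cardiac perforation, cardiac tamponade, and embolic events". Its footnote puts the risk of those transseptal events below 1%.

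**The concern.** Entry to the safety set depends on something that happens after randomisation and after the hazard has begun. The safety outcome itself can prevent it: a serious access or transseptal complication may stop the case before the qualifying catheter goes in, and the subject then leaves the analysis because of the event that the endpoint is meant to count.

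At stake is whether the primary safety result describes the risk of undergoing the procedure, or only the risk among those who got as far as catheter insertion. The second is lower by construction. The catheter condition does this on its own; it would still do so if the eligibility condition in the same sentence were deleted.

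**Working it through.** **No figure to reproduce.** The power and sample size section is redacted and the protocol states no expected SAE rate. The check is a reading of the definitions, followed by an illustration of size.

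**1. Sequence.** Randomisation follows screening and consent (8.4). The procedure clock starts at the first sheath (10.2, Table 7). A mapping or ablation catheter can go in only after access. Section 10.2 A leaves the order of the next steps open, speaking of "The insertion of the FIRMap catheter or performing transseptal puncture, whichever comes first".

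**2. One record under the rule.** A randomised subject suffers a perforation at transseptal puncture, or an access bleed needing surgical repair, and the case is stopped with no mapping or ablation catheter inserted. Section 11 requires the event to be recorded. Section 16.1 places the subject outside the set. In 16.2 C, n counts event-free subjects and N counts the set. Scored properly, this subject is a failure: in N but not in n. As written the subject is in neither, so n/N is too high. The same follows for 16.2 D.

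**3. How many events could be lost.** Inputs: up to 350 subjects randomised 1:1 (6.1), so 350 / 2 = 175 per arm; transseptal risk below 1% (11.3). The ceiling is 175 × 1% = 1.75 per arm. Only events that abort the case before a qualifying catheter are lost. That share is not in the protocol, so a range is assumed: a quarter, a half or all of a 1% risk.

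| Assumed risk r of a lost SAE | Expected per arm, 175 × r | Chance of at least one in 350, 1 − (1 − r)^350 |
|---|---|---|
| 0.25% | 0.44 | 58% |
| 0.5% | 0.88 | 83% |
| 1% | 1.75 | 97% |

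The last row is an extreme for transseptal events: it takes the risk at a bound that the protocol says is not reached and has every event end the case early. Access-site SAEs would add to these numbers, but the protocol gives no rate for them.

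**4. Effect on a reported rate.** With e true event subjects in an arm of 175 and k of them lost, the reported rate is (e − k)/(175 − k). The values of e are assumptions.

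| e (true rate) | k = 1 | k = 2 |
|---|---|---|
| 4 (2.29%) | 3/174 = 1.72% | 2/173 = 1.16% |
| 7 (4.00%) | 6/174 = 3.45% | 5/173 = 2.89% |

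Each lost subject lowers the arm's rate by about 0.55 percentage points.

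**5. Difference between arms.** If both arms lose the same number, both rates are understated and no difference appears. If only controls lose subjects and true event counts are equal, the spurious difference is 0.55 points for one loss at e = 7 (uncorrected chi-square p = 0.79) and 1.11 points for two (p = 0.57). At e = 4 with two losses it is 1.13 points (p = 0.42). None of these comes near significance.

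**The case against.** The events are not hidden. All adverse events are recorded from enrolment and the time of the procedure (section 11), SAEs go to the sponsor within 24 hours and are reviewed by the medical monitor and the monitoring board (11.2), and the DMC reviews data independently (13.5). This is true, but it does not put the event back into the primary comparison.

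A reader might infer that the rule biases the comparison against FIRM: a FIRM subject could have the FIRMap catheter in the right atrium before transseptal puncture and so be counted, while a control with the same complication would not. The documents do not establish this.

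- The protocol does not define a mapping catheter.
- Table 6 lists reference catheters, FIRMap among them, ahead of left atrial access and does not restrict them by arm.
- Inducing AF by burst pacing, typically from the coronary sinus, may put a catheter in place early in either arm.
- Section 10.2 A also lets transseptal puncture come before FIRMap, in which case FIRM subjects are lost in the same way.
- A FIRM subject aborted at puncture is in the set only if sustained AF during the procedure (inclusion criterion 7) had already been shown.

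A reader might also infer that a large share of the control arm's SAEs would vanish. That would require transseptal events to occur at their stated ceiling and nearly all of them to abort the case before any qualifying catheter. Nothing in the protocol supports it.

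Two further points stand as qualifications. The statistical analysis plan is not at hand and might add a safety set, although 16.1 already fixes the set for the primary endpoints. And section 8.3, together with 10.2, taken literally, puts randomisation after all criteria are met, including the intraprocedural one. On that reading fewer randomised subjects could be lost this way. The point relies on section 8.4, which places randomisation after screening assessments.

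**Conclusion.** The point holds as a gap in the safety denominator. Under 16.1 and 16.2, a procedure-related SAE that aborts the case before a mapping or ablation catheter is inserted counts in neither primary safety analysis, and procedural risk is understated. The conclusion rests on the wording of 16.1 and on randomisation preceding the procedure (8.4).

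The absolute effect is probably small: fewer than 1.75 transseptal events per arm of 175 on the protocol's own bound, only some of which would be lost, plus an unquantified number of access events. Each lost subject moves an arm's rate by roughly half a percentage point. A difference between arms is possible if FIRMap precedes transseptal puncture and controls have no qualifying catheter by then, but it remains a possibility only. The rule should be corrected because the safety outcome should not decide who enters the safety analysis, and because membership now turns on an undefined term.

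**What to change.** In 16.2 C and D, replace the ITT denominator with a safety set: all randomised subjects in whom the index procedure was started, meaning that a first vascular access was attempted, analysed by assigned arm. Inclusion should not depend on whether a mapping or ablation catheter was later inserted, or on whether intraprocedural eligibility was confirmed. The second clause is needed because a case stopped before sustained AF is shown would otherwise still drop out through the eligibility condition. Add to 16.1 that its set does not apply to the two safety endpoints; the effectiveness analyses can keep it.

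The cost is a sentence in 16.1 and one each in 16.2 C and D. No new data are needed, because adverse events are already collected from the time of the procedure. The downside is that reported SAE rates may be slightly less favourable.
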